### **5. Relevance to Veterans Health**

PTSD is a prevalent condition for which veterans frequently seek treatment in the VA healthcare system. There are a number of first-line PTSD treatment approaches available, such as Prolonged Exposure and Cognitive Processing Therapy. However, the efficacy rates of these treatments is not as high as what has been observed with civilian populations (e.g., Hoge, 2016; Steenkamp et

al., 2015) and approximately 36% of individuals drop out of these treatments prematurely (Imel et al., 2013). In addition to these efficacy and treatment dropout concerns, implementation barriers have been noted among VA mental health providers (e.g., Finley et al., 2015), with clinical care demands in combination with limited staff resources cited as a barrier to implementation. Taken together, these issues underscore the need to identify alternative treatment approaches that address the barriers cited by both patients and providers. Written Exposure Therapy (WET) is one potential alternative treatment approach that addresses these barriers. WET is a five session treatment that has demonstrated efficacy and is associated with low treatment dropout rates (e.g., 5-10%). If WET is found to be non-inferior relative to the more time intensive Prolonged Exposure in the treatment of veterans with PTSD, then VA would be able to recommend its use for the veteran population.

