## 6. Study Design

The proposed study will use a non-inferiority design to examine whether WET is non-inferior to Prolonged Exposure (PE), a first-line treatment for PTSD that is frequently used by VA treatment providers and is more time intensive.

The study will take place at three sites: VA Boston Healthcare System (VABHS), which has two PTSD clinic (PTC) clinics (Jamaica Plain and Brockton campuses), Ralph H Johnson (RHJ) VAMC PTC clinic, in Charleston, South Carolina, and William S. Middleton Memorial Veterans Hospital, Madison, WI. Veterans will be randomly assigned to either WET ( $n = 90$ ) or PE ( $n = 90$ ). Assessments will be conducted at baseline, and 10-, 20-, and 30- weeks post first treatment session. PTSD symptom severity, acquired through the use of a clinician-administered structured interview, will serve as the primary outcome variable.

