## INTERVENTIONS

**Written Exposure Therapy (WET).** The WET condition consists of 5 weekly treatment sessions, with the first session lasting 1 hour and each subsequent session lasting approximately 40 minutes. The first session consists of education about common trauma reactions and the WET rationale. The participant is then given general instructions for completing the trauma narratives and specific instructions for completing the first 30-minute narrative writing session. All WET sessions begin with the therapist reading the specific writing instructions, clarifying any questions the person has, and leaving the instructions with the participant during the 30-minute writing session. Writing instructions begin with a focus on the details of the trauma and then shift to the meaning of the trauma event. After 30 minutes of writing, the therapist stops the writing and conducts a 5-10 minute check-in regarding how the writing session went for the participant. In

response to VA clinician feedback indicating that veterans sometimes avoid writing about traumatic event in the first and sometimes second writing session, we will permit up to an additional two sessions to course correct in such situations. Specifically, if the veteran does not follow writing instructions in the first and/or second session, these sessions should be repeated to allow for necessary level of exposure to the traumatic event. However, additional sessions will not be provided even if patients continue to partially or fully avoid (i.e. do not follow writing instructions).

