in PTSD symptoms across the full assessment period. The hypothesized moderators (age, sex, combat era, social support, time since index trauma event, and estimated IQ) will then be specified as predictors of the slope factor in separate models. These LGM will be conducted for the full sample first, and will then be conducted separately within each treatment condition to examine whether moderators of treatment outcome are consistent across WET and PE. To aid in the interpretation of clinical significance, results from LGM analyses will be converted to effect size metrics within 95% confidence intervals following established procedures (Feingold, 2015). Evaluation of model fit in the LGM models will be examined using fit diagnostics (i.e., standardized residuals) and common fit statistics (i.e., root mean square error of approximation) following the associated cutoff criteria recommended by Hu & Bentler (1999).

We will conduct additional exploratory analyses to evaluate characteristics of patients who require additional WET sessions, as well as characteristics of patients who require more than 12 PE sessions. These analyses will be conducted using logistic regression with dependent variable being more than 12 sessions of PE or more than 5 sessions of WET (conducted separately for each treatment condition). We will include characteristics such as age, time since trauma event, combat era, baseline PTSD symptom severity, baseline depression, baseline social support, baseline estimated IQ.

**Aim 4:** Follow standard practice for examining secondary outcome measures in a non-inferiority trial (e.g., Thompson-Hollands et al., 2018), we will use hierarchical linear modeling (HLM; Raudenbush & Bryk, 2002) to determine impact of treatment on functional impairment as measured by the WHOQOL-BREF. Analyses will be conducted using an autoregressive covariance matrix at level 1 (within person) and a scaled identity matrix at level 2 (between persons). A between-treatments variable will be included in the analysis, as functional impairment is a secondary outcome and therefore not subject to the same noninferiority analyses. Guidelines from Cohen (1988) will be used to interpret the within- and between-condition effect sizes ( $d$ ).

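### Exploratory session-number models: if the seven characteristics enter jointly in 90 patients per arm, ordinary logistic regression overstates the associations, and Firth penalisation is a cheap improvement

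*Combined protocol and SAP*

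**What the plan says.** The analysis is in Section 9 (Statistical Analysis Plan), Aim 3, in the paragraph after the latent growth models. It is labelled exploratory: "We will conduct additional exploratory analyses to evaluate characteristics of patients who require additional WET sessions", with a parallel analysis of patients who need more than 12 PE sessions. The models are "conducted using logistic regression with dependent variable being more than 12 sessions of PE or more than 5 sessions of WET", and they are "conducted separately for each treatment condition". On predictors the plan says: "We will include characteristics such as age, time since trauma event, combat era, baseline PTSD symptom severity, baseline depression, baseline social support, baseline estimated IQ". The list is open-ended.

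Section 6 (Study Design) fixes 90 patients per arm. The WET event arises when an early session is repeated. The Interventions section explains that this was allowed because "veterans sometimes avoid writing about traumatic event in the first and sometimes second writing session". No frequency is given for that event, or for PE courses beyond 12 sessions.

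The plan does not say whether the characteristics enter one model or several, how combat era is coded, how many events are expected, or what happens if events are few. Section 9 names SPSS and Mplus, with direct maximum likelihood or multiple imputation for missing data. Those methods deal with missing values and do nothing about small-sample bias in a logistic model.

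**The concern.** Logistic regression fitted by maximum likelihood is biased away from an odds ratio of 1 when there are few events per coefficient. If events are rare enough, a coefficient may have no finite estimate at all (separation). Here each model has at most 90 patients and seven or more coefficients, and the rarer outcome class cannot exceed half the arm.

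The purpose is to describe which veterans need more sessions. Section 9 also says that conclusions from all analyses will rest on the size of effects as well as on significance, so overstated odds ratios would feed directly into what is reported. No hypothesis, sample size or non-inferiority conclusion depends on these models.

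**Working it through.** There is no planned figure to reproduce, because the documents give no event count, event rate or power for these models.

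**Inputs from the documents.** 90 patients per arm (Section 6). Seven named characteristics, fitted by arm (Section 9). All randomised participants are analysed for Aims 1 and 3 (Section 7, Assessment Schedule).

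**Assumptions.** Joint entry; event rates from 10% to 50%; combat era with two levels (seven coefficients) or three (eight); the correlations and true effects stated below.

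**Step 1: joint or separate entry.** In the paragraph just before, the moderators in the latent growth models are entered one per model, and the text says so. The logistic paragraph has no such wording and simply says the characteristics will be included. The contrast favours joint entry but does not settle it.

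**Step 2: events per coefficient** = min(events, non-events) / coefficients, at n = 90.

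| Event rate | Events | 7 coefficients | 8 coefficients |
|---|---|---|---|
| 10% | 9 | 9/7 = 1.3 | 9/8 = 1.1 |
| 20% | 18 | 18/7 = 2.6 | 18/8 = 2.3 |
| 30% | 27 | 27/7 = 3.9 | 27/8 = 3.4 |
| 50% (maximum) | 45 | 45/7 = 6.4 | 45/8 = 5.6 |

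With one single-coefficient predictor per model, 10 events among 90 (11%) already give 10 per coefficient.

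**Step 3: bias of the ordinary fit, n = 90, true log odds ratio 0.50 per SD for baseline PTSD severity.** Over seven and eight coefficients and event rates of 10-50%, the mean estimate was 0.54-0.64. The overstatement was about 9-19% at rates of 20-50% and about 27% at 10%. Two independently coded eight-coefficient runs (1000 trials per cell; assumed correlations of 0.6 for PTSD with depression, 0.6 for age with time since trauma, and -0.3 for depression with social support) gave:

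| Event rate | Mean log odds ratio | No finite estimate or no convergence |
|---|---|---|
| 10% | 0.62, 0.64 | 19.5%, 12.8% |
| 20% | 0.57, 0.59 | 1.8%, 0.6% |
| 30% | 0.58, 0.58 | 0.4%, 0% |
| 50% | 0.57, 0.57 | 0.1%, 0% |

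At a 10% rate these means are 0.62/0.50 = 1.24 and 0.64/0.50 = 1.28 times the truth. With seven coefficients, about 2% of trials at a 10% rate had no finite estimate.

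**Step 4: sensitivity to the assumptions.** A further simulation used 2000 replicates per cell, pairwise correlations of 0.2 and a true odds ratio of 1.8.
- Seven coefficients: overstatement of 12-17% at rates of 20-50% and 29% at 10%. No finite estimate in 3.4% of replicates at 10%, and in none of 2000 at 20% or above.
- Eight coefficients: overstatement of 13-22% at 20-50% and 31% at 10%. No finite estimate in 18.0% at 10%, 1.7% at 20%, and 0.2% or fewer from 30%.
- Coverage of individual 95% intervals was 94.5-95.6% at rates of 10-50%.

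**Step 5: size on the odds-ratio scale.** The true value is exp(0.50) = 1.65. A mean log odds ratio of 0.57 corresponds to exp(0.57) = 1.77, which is exp(0.07) = 1.07 times the truth. An overstatement of 27% (0.635) corresponds to 1.89, or exp(0.135) = 1.14 times the truth.

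**Step 6: Firth penalised likelihood in the Step 3 setting.** The mean estimate was 0.48-0.50 over seven and eight coefficients and rates of 10-50%. Root mean squared error was 12-30% lower than for the ordinary fit in every cell.

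**The case against.** The strongest reply is that the ordinary fit works tolerably. At event rates of 20% or more, estimates almost always exist and individual intervals cover at close to 95%. Ten events per coefficient is a rule of thumb and not a condition for an estimate to exist. At a 50% rate the standard error for a standardised predictor is at least 1/sqrt(90 x 0.5 x 0.5) = 0.21, three times the bias of 0.07. All of this stands. It rules out an inference a reader might draw from the events-per-coefficient ceiling, that no event rate could support ordinary maximum likelihood.

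A second reply is that joint entry is nowhere stated, and that with one predictor per model the problem largely disappears. This also stands, so the point is conditional. Firth fitting does no harm if predictors enter singly.

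A third concerns the denominator. Section 5 says that "approximately 36% of individuals drop out of these treatments prematurely", and a reader might infer that only about 90 x (1 - 0.36) = 58 PE patients are usable, which would make the bias much larger. The documents do not support that. Section 7 includes all randomised participants for Aim 3, a dropout's session count is observed, and the 36% describes first-line treatments in general and not PE in this trial.

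Finally, the event rates are unknown. The Interventions section says only that early avoidance sometimes happens, which is not a rate. The 10% case is a possibility and not a forecast.

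**Conclusion.** The concern holds as a cheap improvement to an exploratory analysis. If the seven characteristics enter jointly, ordinary maximum likelihood in 90 patients per arm is biased away from 1 at every event rate examined: about 9-19% on the log odds scale at rates of 20-50%, and about 27% at 10%. Under the alternative simulation assumptions the figures are a few points higher. Missing estimates are a practical risk only when the event is uncommon: at a 10% rate, about 2-3% of trials with seven coefficients and 13-20% with eight, against 2% or fewer at 20% or above.

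The ordinary fit is therefore usable at common event rates, and the plan is not unworkable as written. The figures rest on joint entry, assumed event rates, assumed correlations and effect sizes and, for the eight-coefficient results, an assumed three-level combat era. The means for the ordinary fit are taken over fits that converged. The primary conclusion of the trial is untouched.

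**What to change.** In Section 9, Aim 3, replace the logistic-regression sentence for these two models with wording such as:

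> Within each arm, in all randomised participants, the listed baseline characteristics will be entered jointly in a Firth penalised-likelihood logistic regression. Odds ratios will be reported with profile penalised-likelihood 95% confidence intervals, together with the number of events and the number of coefficients in each model.

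The same sentence should close the list of characteristics and state the coding of combat era.

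The cost is small: no extra patients or data. The odds ratios will be slightly smaller than from an ordinary fit, and the routine lies outside the default SPSS and Mplus menus. If baseline characteristics are missing, the estimates must be pooled across imputations, and the plan should say how. With all randomised participants as the denominator, a patient who leaves early counts as not exceeding the session threshold. The report should therefore describe the outcome as sessions received.

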**Assessment Schedule.** Participants will be assessed by an IE at baseline, 10-, 20- and 30-weeks post first treatment session. This study has a challenge of two treatments that possess substantially different number of sessions (e.g., 5 vs 8 to 15). The use of post-treatment assessment would be problematic given that participants in the two treatment conditions would be completing treatment at substantially different time from baseline assessment, with time to post-treatment being significantly greater in the PE condition than the WET condition. This is problematic as differences in outcome could be attributable to time since baseline assessment rather than treatment differences. Thus, in order to assure that time does not serve as a confound, assessments in this study will occur at equal intervals from baseline for both treatment conditions. Although we would expect that the majority of PE participants would complete treatment by the 10 week assessment period, it is well-documented that for CPT and PE the time to complete treatment varies substantially across participants, even when the treatment protocol is to attend twice weekly sessions (Gutner et al., 2016). In our prior study we requested participants attend twice weekly sessions for CPT but even with this system in place only 65% of the CPT participants completed treatment in 12 weeks and only one participant out of 63 completed treatment in 6 weeks (see Sloan, Marx, & Lee, 2018 for a discussion of this issue).

Participants in both treatment conditions will be considered a “treatment drop out” if they do not attend all treatment sessions. Consistent with the intent-to-treat approach, any participant who drops out will be asked to complete all assessments and all participants who are randomized will be included in data analyses for Study Aims 1 and 3. Treatment expectancy, credibility and satisfaction will be assessed to ensure that acceptability and feasibility of WET continues to be high with the veteran sample

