**Prolonged Exposure (PE).** PE is designed to be delivered in weekly 90 minute sessions over 8-15 sessions. The sessions are flexible according to the response of the patient. Stopping before 15 sessions should occur because (1) the patient has a stable score (i.e., at least two consecutive sessions) below the probable PTSD diagnosis cut score of 33 (Bovin et al., 2016) and (2) the clinician and patient agree that substantial clinical gain has occurred and no additional sessions are needed. Up to 15 sessions are provided if the score remains above the probable PTSD cut score. Treatment response is determined based on PCL-5 measure administered at each treatment session. The conceptual foundation of PE is based upon emotional processing theory (Foa & Kozak, 1986). The PE model proposes that chronic PTSD develops when there is a failure to process the traumatic memory because of extensive avoidance of trauma reminders. PE mimics the natural fear modification process. During PE, patients are encouraged to confront (or expose themselves) to safe but anxiety-eliciting situations, in both imagination and *in vivo*, with the goal of overcoming excessive fear and anxiety. Thus, PE includes the following core components: (a) psychoeducation about the common reactions to traumatic events and presentation of the rationale for PE, (b) repeated *in vivo* exposure to situations or objects being avoided due to distress and anxiety, and (c) repeated, prolonged imaginal exposure to memories of the event(s). The focus of treatment initially lies in educating the patient about the PTSD diagnosis, gathering of detailed information about the traumatic event, and providing a sound rationale for PE. Patients' understanding of the rationale for PE is important because recognition of the importance of breaking their patterns of avoidance is a key goal. Patients, together with their therapist develop a hierarchy of feared but safe trauma related situations and objects and are instructed to gradually approach these situations between sessions (*in vivo* exposure exercises). The structure of gradual exposure is fairly consistent with traditional exposure-based interventions such that anxiety-provoking stimuli (e.g., physical or verbal cues) are presented gradually. The 3rd component of treatment is imaginal exposure. During this phase, therapists assist patients in repeatedly recounting their traumatic event in detail, including their thoughts, feelings, and reactions that occurred during the event(s). Imaginal exposure is conducted during sessions and is audiotaped for patients to listen to at home between sessions.

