
## 9. Statistical Analysis Plan

Data will be analyzed in SPSS and MPlus software, which licenses are obtained by the Behavioral Science Division of the National Center for PTSD at VA Boston. The software is stored on a password protected server that is behind the VA firewall.

The equivalence of the treatment conditions will first be assessed according to key baseline variables (demographics and outcome variables) using t-tests, nonparametric equivalence, or Chi-square tests, depending on the type (continuous or dichotomous) and distribution (normal or

non-normal) of the data. Any variables that differ among groups will be used as covariates in the final analyses.

We anticipate some participant attrition during the trial. If a subject drops out of the study for any reason, we will vigorously pursue follow-up to minimize missing data. Yet, some data will inevitably be missing. Missing data will be handled in all analyses using direct maximum likelihood or multiple imputation techniques within MPlus 8.0 (Muthén & Muthén, 2018) under a missing at random (MAR) assumption. Modern missing data techniques such as direct ML increase statistical power and provide more accurate estimates of model parameters and standard errors, and are the recommended intent-to-treat approach for clinical trials (Enders, 2010). The primary analyses in this study will be performed on the intent-to-treat population that includes all patients randomized to a condition. Supplementary analyses will also be conducted examining outcomes in the subset of participants who complete a full course of treatment in each condition. In order to better understand the potential reproducibility of our findings, our conclusions from all analyses will be based on both the statistical significance of parameters and the magnitude of associated effect sizes.

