In the event that a participant experiences an increase in PTSD symptom severity but without suicidal/homicidal risk, the PI or site PI will intervene by asking direct questions about the nature and causes of the distress, conduct a PTSD assessment, and schedule extra contacts (assessments) if deemed necessary. Such individuals will be withdrawn from study treatment from the protocol if they report a substantial increase in the PTSD symptom severity (i.e. at least 10 points higher than their baseline PTSD symptom severity score) that is sustained over a three-week period and the cause of the increase is determined to be related to the study treatment. We have selected

the 10-point increase and 3-week time frame based on Foa, Zoellner et al. (2002) in which they emphasize the importance of using a reliable index score when considering increases (and decreases) in PTSD symptoms. Importantly, Foa and colleagues (2002) have reported that only a minority of participants showed an acute substantial increase in PTSD symptom severity during Prolonged Exposure treatment, and that this acute increase was not associated with an increased risk for dropout or poor treatment outcome. Nevertheless, to protect against risk, we will monitor participants for undue distress reactions and will use a 10-point increase from baseline assessment of PTSD symptom severity that is sustained for 3 weeks as a guide for potentially withdrawing a participant from the study treatment. If a participant is withdrawn from the study treatment, they will be followed by study personnel, if they agree to be followed, to ensure that they have received adequate clinical care. In addition, if they agree, the study will continue to conduct assessments with the participant. In addition, participants who are deemed ineligible to enroll in the trial will be referred to the appropriate VA mental health clinic. The PI or site PI will subsequently contact (within one week) these veterans to make sure that they have not experienced any barriers in following through with clinical referrals.

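### The exploratory session-count regressions aim at need for more sessions but count sessions attended, so PE early stoppers fall in with early finishers

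*Combined protocol and SAP*

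**What the plan says.** The last paragraph under Aim 3 in SAP Section 9 sets out to evaluate the "characteristics of patients who require more than 12 PE sessions", and likewise patients who need extra WET sessions. It uses one logistic model per arm, with the "dependent variable being more than 12 sessions of PE or more than 5 sessions of WET". It lists characteristics such as age, combat era and baseline severity. It names no analysis set and does not say how to code a participant who stops early.

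These other parts of the plan bear on the point:

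- **Analysis set.** Section 7, Assessment Schedule: "all participants who are randomized will be included in data analyses for Study Aims 1 and 3". The same paragraph calls participants dropouts "if they do not attend all treatment sessions".
- **PE length.** Section 8, Interventions, describes a flexible course of 8 to 15 sessions. It may end early on a stable PCL-5 score below 33 together with agreement between clinician and patient. Otherwise "Up to 15 sessions are provided if the score remains above the probable PTSD cut score".
- **Withdrawal.** Section 11, Protocol for Managing Adverse Events: "Such individuals will be withdrawn from study treatment from the protocol if they report a substantial increase in the PTSD symptom severity", where the increase is sustained and judged to be related to treatment.
- **WET length.** Section 8: "The WET condition consists of 5 weekly treatment sessions". Up to two further sessions are allowed so that session 1 and/or 2 can be repeated.
- **Missing data.** Section 9: "Missing data will be handled in all analyses using direct maximum likelihood or multiple imputation techniques".

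**The concern.** The question is about need, but the outcome is a number of sessions. For anyone who stops early the two differ.

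In PE, someone who quits at session 4, someone withdrawn at session 9 because symptoms rose, and a responder who finishes at session 10 all have 12 sessions or fewer. All three are coded 0. Only the third is known not to have needed more than 12. A characteristic associated with quitting is therefore pushed towards appearing to predict a shorter required course.

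In WET, a veteran who attends sessions 1, 1, 2 and 3 and then leaves did receive an additional session, but the count is four and the code is 0.

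What is at stake is the description of who needs longer treatment, which is useful to a clinic choosing between a brief and a longer therapy.

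**Working it through.** The documents give no sample size, power or expected rate for these regressions, so there is no plan figure to reproduce. The calculations below are illustrations.

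**Inputs from the documents.** 90 participants per arm (Sections 1 and 6). About 36% dropout (Section 5, for first-line PTSD treatments generally, not PE alone). Attrition up to 50% (Section 3). WET dropout of 5-10% (Section 5).

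**Assumed inputs.** All PE dropout occurs by session 12. A share q = 0.3 to 0.5 of PE completers exceeds 12 sessions. A binary covariate X, split 50:50, doubles the odds of dropping out and has no effect on need, so the true odds ratio is 1.0.

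**1. Make-up of the PE zero group.** The share who are quitters is d / [d + (1 − d)(1 − q)]. With d = 0.36:
- q = 0.3: 32.4 / 72.7 = 0.45
- q = 0.5: 32.4 / 61.2 = 0.53

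**2. Odds ratio under the literal coding.** Overall dropout of 0.36 with a dropout odds ratio of 2 gives 0.281 for X = 0 and 0.439 for X = 1. Then P(>12 | X) = (1 − d_X) × q.
- q = 0.3: 0.216 and 0.168. OR = (0.168/0.832) / (0.216/0.784) = 0.736 from unrounded values
- q = 0.5: 0.359 and 0.281. OR = 0.695
- At 20% dropout (assumed) the range is 0.80-0.84. At 50% it is 0.63-0.67.

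**3. Bias against noise.** With 45 participants at each level of X, the standard error of the unadjusted log odds ratio is the square root of the sum of the reciprocals of the four expected cell counts.
- q = 0.3: √(1/7.6 + 1/37.4 + 1/9.7 + 1/35.3) = 0.54. Bias |ln 0.736| = 0.306, and 0.306/0.54 = 0.57
- q = 0.5: √(1/12.6 + 1/32.4 + 1/16.2 + 1/28.8) = 0.45. Bias |ln 0.695| = 0.364, and 0.364/0.45 = 0.80

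The bias is therefore about 0.6-0.8 of one standard error.

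**4. How much bias a restricted analysis removes.** Removing early stoppers from the zero group gives OR 1.0 in the scenario above, because quitting there does not depend on need. A less favourable scenario assumes a constant per-session dropout hazard, h for X = 0 and 2h for X = 1, solved to give 36% dropout overall. A share q needs 15 sessions and the rest finish at session m = 8 to 10. Events are q(1 − h_X)^12 and finishers are (1 − q)(1 − h_X)^(m − 1).
- Literal coding: OR 0.595-0.645
- Events against finishers only: OR 0.838-0.921

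Some bias remains because patients who need more sessions are exposed to dropout for longer.

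**5. WET bound.** Anyone who completes the five planned sessions plus a repeat exceeds five and is coded 1. Only a participant who had a repeat and left at or before five attendances is miscoded. At 5-10% dropout, the ceiling is 0.10 × 90 = 9, reduced to those who had a repeat. The documents do not give the share with a repeat.

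**The case against.** The strongest reply is that the plan leaves the coding unspecified rather than wrong. The all-randomised sentence follows one about asking dropouts to complete assessments, so it can be read as an intent-to-treat rule for assessed outcomes. The session-count models are introduced as additional exploratory analyses, and it is only their position under Aim 3 that brings them under that rule. If the outcome is need, a quitter's value is unobserved and the missing-data rule could apply.

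Part of this stands: coding PE quitters as 0 is an inference from the text, and no sentence of the plan states it. But the dependent variable is written as a number of sessions, and a quitter's count is observed, so the missing-data rule does not clearly reach it. If the models fall outside Aim 3, no analysis set is stated at all.

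The second reply is that the bias is smaller than the sampling error and depends on undocumented inputs. This stands too. Across both scenarios and 20-50% dropout the literal odds ratio runs from 0.46 to 0.84, so the documents fix the mechanism but not the size.

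Third, restricting to those who stayed conditions on behaviour after randomisation. That is fair, and it is why a three-category outcome is an equally defensible choice.

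A reader might also infer that the five-session definition of a full WET course under Aim 2 conflicts with the permitted repeats and so endangers the dropout comparison. The documents do not support this. Section 8 describes repeats within a five-session treatment, and with the dropout definition in Section 7 this favours reading the phrase as the five planned sessions. It is a matter of wording.

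**Conclusion.** The point holds as a minor one. As written, the outcome does not measure what the paragraph sets out to describe. On the literal reading, the PE zero group mixes early stoppers with early finishers. At 36% dropout and the assumed inputs, quitters are 45-53% of that group, and a covariate unrelated to need shows an odds ratio of 0.69-0.74. The downward direction follows for any characteristic that raises quitting and leaves need unchanged; the size rests on the assumptions listed. The WET effect is small, with a ceiling of about 9 of 90 if dropout matches the plan's 5-10%.

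A reader might infer that the trial's main results are compromised, or that these regressions would yield a demonstrably false finding. Neither follows. The analyses are labelled exploratory and feed neither the non-inferiority conclusion nor Hypothesis 2a. In the main illustration the bias is below one standard error.

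**What to change.** **(a) PE regression.** Do not code as 0 a participant who stopped at or before session 12 without finishing under the Section 8 rule. Either compare those who finished under that rule by session 12 with those who attended more than 12 sessions, or use a three-category outcome with early stopping as its own category. Tabulate early stoppers by the same characteristics. For the restricted comparison, state that the result applies to those who stayed and that some selection bias remains.

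**(b) WET regression.** Replace the more-than-five count with receipt of a repeat of session 1 or 2. Note that a participant who left before a repeat could be given is still coded 0.

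**Cost.** A few SAP sentences and recoding of session records. The restricted PE model loses about 30-32 non-events and no events. In the simple scenario at 36% dropout, 90 − 32.4 = 57.6 participants remain, and the standard error rises from about 0.45-0.54 to about 0.53-0.58. The model is fragile either way: 15-29 events across the two scenarios is 2.1-4.1 per covariate if all seven listed characteristics enter together, which the plan does not specify.
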